## **Implementing Womb-like Environments in NCUs**

**SHORT TITLE/ACRONYM**

Final outputs will be implemented and tested in incubators, initially without infants (as part of WP1). Once extensively tested, the system will be introduced to incubators with infants having parental consent.

Participants. A total of 150 infants will be tested, accounting for a 20% attrition rate due to multiple experiments (10%) and longitudinal design (10%). This ensures sufficient participants per group (WS-PTg, SC-PTg, CO-FTg) for statistical analyses ( $\alpha=0.05$ , power=0.80, GPower 3.1). The estimate is based on effect sizes ( $d=0.59-0.80$ ) from prior studies on early speech perception and language outcomes in preterm infants. Participants will include:

- 1) Womb-simulated PT group (WS-PTg): Forty healthy preterm infants meeting five primary criteria:
  1. Gestational age  $\geq 26$  and  $\leq 34$  weeks.
  2. Absence of major cerebral damage (e.g., periventricular leukomalacia, intraventricular haemorrhage...).
  3. No indication of visual or hearing impairment.
  4. No family risks of developmental or language disorders.
  5. From monolingual English-speaking families.

Infants eligible to participate in the WS-PTg will be identified by the NCU team as soon as possible after their arrival to the unit and parents of these infants will be approached by one of the neonatal nurses to ask if they would want to take part in the project. Families who have given consent will be approached by the research team and given the necessary equipment to do the audio recordings. Meanwhile, a general recording of infant-directed speech recorded by the research team will be used until parental recordings are available. Infants will be exposed to the recordings until they are discharged from the NCU or they reach their due date.

- 2) Standard care PT group (SC-PTg): Forty healthy preterm infants who meet the same criteria outlined above will be recruited using the same strategy. Infants assigned to the SC-PTg will, when possible, be those who have already been discharged from the NCU.
- 3) Comparison FT group (CO-FTg): Forty healthy full-term infants born at  $\geq 37$  weeks who also meet criteria 2–5 outlined above.

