**SHORT TITLE/ACRONYM**

**Predictions:** Based on previous findings Preterm groups are expected to show delayed acquisition of these properties compared to the full-term group. If, as predicted, the delay stems from a lack of prenatal prosody exposure, the delay will appear in the Standard-Care-group but not in the Womb-Simulated-group.

**Analyses:** Data on looking times, vocabulary, and cognitive development will be collected and compared across the three study groups. Analyses will be conducted using linear mixed-effects models, which are particularly suitable for handling missing data in longitudinal studies with repeated measurements.

Analyses will be conducted using R and the lme4 package to fit linear mixed-effects models. Fixed effects will include Group (womb-simulated preterm, standard-care preterm, full-term), Age (7.5, 9, 10.5, 12 months), and Stimulus Type (e.g., alternating vs. non-alternating). Participants and stimuli will be included as random effects. Model selection will follow a stepwise comparison approach, retaining the model with the lowest BIC and a significant log-likelihood ratio test. A typical model will take the form:

`lmer(TotalLook~Group*Age*StimType+(Age|SubjectID)+(1|Stimulus)).`

P-values will be derived from F-values using the Satterthwaite approximation. Planned comparisons will use orthogonal contrasts. While SES, gestational age, and birth weight will not be included in the primary models, their effects will be explored in secondary analyses. All analyses will be pre-registered and conducted in line with open science practices.

Data will be summarised using descriptive statistics and visualised with graphs to illustrate group differences and developmental trajectories. Demographic matching of full-term infants will further strengthen causal inference by reducing potential confounding factors.

**Dissemination Activities:** Co-designed resources such as infographics, videos, animations, and a website will target families and practitioners. Workshops for families, practitioners, and

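### The typical mixed model has no by-infant random slope for StimType, so its Group-by-StimType test is anti-conservative if infants differ in stimulus preference

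*Protocol*

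**What the plan says.** Section 3 (Analyses) says in words that "Participants and stimuli will be included as random effects", naming no slopes. It then prints a formula, introduced by "A typical model will take the form": "lmer(TotalLook~Group*Age*StimType+(Age|SubjectID)+(1|Stimulus". So each infant has a random intercept and a random Age slope, and each stimulus a random intercept. No by-infant term for StimType appears anywhere in the protocol.

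Two further sentences bear on the point. On building the model: "Model selection will follow a stepwise comparison approach, retaining the model with the lowest BIC and a significant log-likelihood ratio test". The candidate terms are not listed. On testing: "P-values will be derived from F-values using the Satterthwaite approximation". The text also commits to pre-registering all analyses.

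The prediction that the model serves is that "the delay will appear in the Standard-Care-group but not in the Womb-Simulated-group".

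**The concern.** Each prosody task is scored by how much longer an infant looks for one stimulus type than for the other. The group question is whether that within-infant difference itself differs between groups. The unit that carries information on it is the infant: more trials measure one infant's preference more precisely, but do not supply more infants.

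In the printed model, all infants in a group share the same StimType effect at a given age. Real differences in preference between infants then have no variance component of their own. StimType is balanced within each visit (Fig. 3: 4 and 4 trials for tone, 8 and 8 for stress), so the infant intercept and the Age slope cannot absorb them. The model ignores the correlation of an infant's stimulus-type difference across trials and visits, and judges Group-by-StimType almost entirely against trial-level residual noise. The Satterthwaite method sets degrees of freedom for the variance components in the model; it cannot supply one that is missing.

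At stake is a claim that the womb-like environment changes prosody perception when the groups differ only by chance in which infants they contain.

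**Working it through.** **Inputs from the protocol.** Three groups of 40 (section 3, Participants, e.g. "Forty healthy preterm infants meeting five primary criteria"); alpha 0.05; visits at 7.5, 9, 10.5 and 12 months; trials per stimulus type per visit of 4 (tone) and 8 (stress), from Fig. 3.

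**Assumptions.** Each task is run at all four visits; 40 infants per group are complete; trial-level looking times are analysed; Age is numeric and centred; an infant's preference is stable over visits. Let r be the between-infant SD of the StimType effect divided by the residual trial SD. The protocol gives neither SD, so r is varied.

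**The plan's own figure.** 3 x 40 = 120, and 120/0.80 = 150, as stated. With a two-sided t test and the infant as unit, 40 per group gives 80% power at about d = 0.64, inside the stated range of 0.59 to 0.80. The sample size is thus consistent with infant-level comparisons.

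**Inflation of the F statistic.** With n_t trials per type per infant, an infant's mean difference has variance 2/n_t from trials (residual variance 1) plus r^2 from preference. Relative to trial noise alone the ratio is a = 1 + n_t r^2/2. Without the slope, the residual variance absorbs a little of this: s2 = (117a + dfE)/(117 + dfE). Here 117 = 120 infants - 3 groups, and dfE is about 3,231 for tone and 7,071 for stress. F is inflated by L = a/s2, and the type I error of the 2-df test is about 0.05^(1/L).

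Tone, n_t = 4 x 4 = 16, r = 0.2: a = 1 + 16 x 0.04/2 = 1.32; s2 = 1.011; L = 1.31; 0.05^(1/1.31) = 10.1%.

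Stress, n_t = 8 x 4 = 32, r = 0.2: a = 1 + 32 x 0.04/2 = 1.64; s2 = 1.010; L = 1.62; 0.05^(1/1.62) = 15.8%.

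| r | Tone: L | Tone: type I error | Stress: L | Stress: type I error |
|---|---|---|---|---|
| 0 | 1.00 | 5.0% | 1.00 | 5.0% |
| 0.1 | 1.08 | 6.2% | 1.16 | 7.5% |
| 0.2 | 1.31 | 10.1% | 1.62 | 15.8% |
| 0.3 | 1.68 | 16.8% | 2.38 | 28.5% |
| 0.5 | 2.80 | 34.4% | 4.69 | 52.8% |

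**Simulation check.** Mixed models fitted without the slope at r = 0, 0.2, 0.3 and 0.5 rejected in 5.8, 9.8, 17.5 and 37.5% of runs for tone (400 runs each) and 5.6, 17.6, 29.2 and 56.4% for stress (250 runs each). With the slope added, the range was 4.8 to 6.2%. The printed formula in lme4 (tone, 144 to 200 runs) gave 4.0, 9.0, 25.5 and 31.9%, and 4 to 6% with the slope. The 25.5% at r = 0.3 lies above the formula; a repeat with 4,866 fits gave 16.8%, which agrees with it.

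**Fewer visits.** Stress at two visits has n_t = 16, the tone count in the table, so about 10% at r = 0.2 and 34% at r = 0.5. At one visit, stress gives about 7% and 20%, and tone about 6% and 11-12%.

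**Three-way term.** A stable preference cancels from an infant's age trend, so only s2 enters and the error is about 0.05^s2. At r = 0.5, s2 is 1.07 for both tasks and 0.05^1.07 = 4.1%. Simulation (4,000 runs) gave 5.0, 4.9 and 4.3% for tone and 5.0, 4.8 and 4.3% for stress at r = 0.2, 0.3 and 0.5. There is no inflation.

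**If the slope were a BIC candidate** (1 or 3 extra parameters), the error after selection would be:
- r = 0.2: 8.5-9.9% (tone), 6.5-13.8% (stress).
- r = 0.3: 5.8-12.2% (tone), 5.0-5.4% (stress).
- r = 0.5: about 5% for both.

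With 3 extra parameters at r = 0.2, BIC keeps the slope in only 0.4% of tone runs and 17% of stress runs.

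**The case against.** The formula is offered as typical, is subject to stepwise comparison, and will be pre-registered. The final random structure could therefore still include the slope. That is fair, but the protocol names no such candidate, and its selection rule would often reject a modest slope, as shown above. Pre-registering the printed line would fix the omission.

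The prediction is of delayed acquisition, and the lexical stress and tone tasks are described as tracking increasing and declining abilities. The three-way term may then be the one that matters, and a stable preference leaves it at or just below 5%. This stands, and limits the finding to the two-way term. A preference that varies from visit to visit would inflate the three-way test, and the model has no term for that either; its size is not worked out here.

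The inflation rests on an SD that the documents do not give and on a four-visit schedule that they do not confirm. Fig. 2 is not shown, and Appendix 2 marks language assessments at every visit without saying which task runs when. This stands too. Zero variation is nevertheless hard to square with the Prosodic Boundaries plan, which asks whether an infant's sensitivity predicts vocabulary at 12 months and so presupposes that infants differ.

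Two stronger readings are tempting. A reader might infer that the model treats repeated trials as independent. It does not: it has an infant intercept, an infant Age slope and a stimulus intercept, and lacks one component. A reader might also infer that the false-positive rate is well above 5% as a property of the plan. The documents do not support that: the rate is 5% if infants share one preference and only 6-8% at a slope SD of 0.1.

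**Conclusion.** The concern holds in conditional form. As printed, the Group-by-StimType test is anti-conservative whenever infants differ in stimulus preference. The error rises from 5% at no variation to 10-16% at a slope SD of 0.2 residual SD and 34-53% at 0.5. These figures are for the three-group 2-df test; a single contrast between two groups is inflated less (at 0.5, about 24% for tone and 37% for stress). They rest on 40 complete infants per group, four visits per task and a stable preference. The size in this trial cannot be read from the protocol, but the direction of the error is certain. Neither the word typical, nor stepwise selection, nor Satterthwaite degrees of freedom removes it. Since the remedy is simple and restores about 5%, the line should be corrected before pre-registration.

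**What to change.** Change the random part to `(Age + StimType | SubjectID) + (1 | Stimulus)`. State that the StimType slope is exempt from BIC and likelihood-ratio selection for any test involving Group-by-StimType. If the model does not converge, simplify to uncorrelated slopes before anything else.

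For the three-way test, add an infant-by-visit StimType term, or an Age:StimType slope within infant, where the data support it.

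As a sensitivity check, compute one preference score per infant per visit and fit `Group*Age + (1|SubjectID)`. It is not an equivalent analysis, because it drops the stimulus random effect.

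The cost is a changed model line and a stated fallback. Standard errors for the group contrast become wider, with about 117 denominator degrees of freedom instead of thousands, and some fits may have convergence problems.

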### **5.2.2 Sampling technique**

A purposive sampling strategy will be used.

- Preterm infants will be identified through the Neonatal Care Unit by the clinical care team based on clearly defined eligibility criteria. This approach ensures that participants meet specific gestational, medical, and family language background requirements relevant to the research question.
- Full-term infants will be recruited through the Oxford Brookes BabyLab participant database, which includes families who have previously expressed interest in taking part in developmental research. Infants will be selected to match the preterm groups on key demographic variables such as age, gender, and socioeconomic background.

This sampling approach is justified by the study's developmental and theoretical framework, which requires carefully defined comparison groups to isolate the effects of early auditory experience on language development. Random sampling is neither feasible nor appropriate in this context, as the study focuses on specific infant populations with well-defined characteristics.

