**Full-term infants and potential standard-care preterm participants recruited outside NCUs**

Full-term infants, and potentially some preterm infants in the standard-care group, will be identified through the Oxford Brookes BabyLab participant database. This database consists of families who have proactively registered their interest in taking part in developmental research and have provided consent to be contacted about future studies.

Recruitment to the BabyLab database occurs via general publicity, including leaflets, posters, and the BabyLab website. These materials advertise participation in BabyLab research broadly rather than a specific study. Eligible families are contacted by email when their child reaches the appropriate age and are then provided with full written and verbal information about the study before any consent is sought.

The researcher will also spend some time in the ultrasound unit where women/partners are waiting for their scans and talk about the study. At this point, parents will receive a flyer and interested parents will be asked to complete an expression of interest card to join the BabyLab Participant Database.

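### The womb-simulated versus standard-care preterm contrast is neither randomised nor matched, yet the primary models leave out gestational age, birth weight and SES, so it is open to confounding by measured variables

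*Protocol*

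**What the plan says.** **Model.** The Analyses paragraph of section 3 gives the typical model as "lmer(TotalLook~Group*Age*StimType+(Age|SubjectID)+(1|Stimulus" (closing brackets omitted here). Its fixed effects are group, age and stimulus type, with no baseline covariate. The omission is deliberate: "While SES, gestational age, and birth weight will not be included in the primary models, their effects will be explored in secondary analyses".

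**Prediction.** Section 3 expects that "the delay will appear in the Standard-Care-group but not in the Womb-Simulated-group". This is a causal reading of WS against SC.

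**How infants enter the two preterm groups.** For WS, section 3 (Participants) says: "Infants eligible to participate in the WS-PTg will be identified by the NCU team as soon as possible after their arrival to the unit". For SC it says: "Infants assigned to the SC-PTg will, when possible, be those who have already been discharged from the NCU". Section 5.3.1 adds a further source for SC alone: "potentially some preterm infants in the standard-care group, will be identified through the Oxford Brookes BabyLab participant database". Sections 4 and 5.3 repeat that database route.

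**Matching.** Section 3 matches the full-term infants to the other groups on gender and SES, and section 5.2.2 adds age. Nothing matches WS to SC, and nothing matches on gestational age or birth weight. The Analyses paragraph then says: "Demographic matching of full-term infants will further strengthen causal inference by reducing potential confounding factors".

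**Eligibility.** Both preterm groups span 26 to 34 weeks of gestation. The full-term group starts at 37 weeks.

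**The concern.** The question the trial exists to answer is whether WS infants do better than SC infants. Without random assignment, that comparison relies on the two groups being alike at the start or on the analysis allowing for differences.

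The shared eligibility criteria leave an eight-week range of gestational age. The timing of recruitment (on arrival against, when possible, after discharge) and the volunteer database could each shift gestational age, birth weight or family background between the groups. The primary model would attribute any such shift to the sound environment.

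Exploring covariate effects in secondary analyses does not commit the team to an adjusted WS-SC estimate, so the headline result would be the unadjusted one. Matching the full-term group does not balance the two preterm groups against each other.

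**Working it through.** **1. The plan's own figures.** Forty per group in three groups is 120, and 120 / (1 − 0.20) = 150, which is the stated total. The stated inputs are α = 0.05, power 0.80 and d = 0.59 to 0.80. A two-sample t-test with 40 per group, two-sided, has power 0.74 at d = 0.59. That value is the reference for step 4. Whether 40 is enough is a separate matter.

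**2. Bias of the unadjusted contrast.** For one covariate, bias in outcome SD = r × g. Here r is the within-group correlation of covariate and outcome, and g is the WS-SC difference in covariate SDs. The protocol gives neither, so both are assumed: r = 0.2 to 0.4, g = 0.3 to 0.5.

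- Low end: 0.2 × 0.3 = 0.06 SD, and 0.06 / 0.59 = 10% of the smallest design effect.
- High end: 0.4 × 0.5 = 0.20 SD, and 0.20 / 0.59 = 34%.

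In weeks: if gestational age were uniform over 26 to 34 weeks (assumed), its SD would be 8 / √12 = 2.31 weeks, so g = 0.3 to 0.5 is about 0.7 to 1.2 weeks. Over a wider range of r, 0.1 to 0.4, a 1-week imbalance gives 0.04 to 0.17 SD and a 2-week imbalance gives 0.09 to 0.35 SD.

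**3. Rejection rate with no true effect.** Noncentral t, 78 df, noncentrality = bias × √(40/2), nominal two-sided 5%:

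| Bias (SD) | Rejection rate |
|---|---|
| 0.06 | 5.8% |
| 0.10 | 7.3% |
| 0.15 | 10.2% |
| 0.20 | 14.3% |

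**4. Power after adjustment.** The variance of the adjusted contrast, relative to the unadjusted one, is (1 − r²) × (1 + g²/4). The first factor is the gain from explained variance. The second is the price of imbalance. Power at d = 0.59 with 40 per group:

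| r | g | Variance ratio | Power |
|---|---|---|---|
| 0.2 | 0.3 | 0.96 × 1.0225 = 0.98 | 0.75 |
| 0.2 | 0.5 | 0.96 × 1.0625 = 1.02 | 0.73 |
| 0.4 | 0.3 | 0.84 × 1.0225 = 0.86 | 0.80 |
| 0.4 | 0.5 | 0.84 × 1.0625 = 0.89 | 0.79 |

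Against 0.74 unadjusted, adjustment may help or cost a little. The case for it is bias, not precision.

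**5. What the adjusted model must look like.**

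- Preterm gestational age ends at 34 weeks and full-term begins at 37. The ranges do not overlap, so in the three-group model gestational age is nearly aliased with group. The adjustment belongs in a preterm-only contrast.
- For looking times the effect of interest lies in group × stimulus type. A covariate main effect shifts looking to both stimulus types alike and leaves that interaction unadjusted, so covariate × stimulus type terms are needed.
- WS exposure runs until discharge or due date, so gestational age also bears on how long a WS infant is exposed. Its slope may differ between WS and SC, and a common slope should be checked.

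Steps 2 to 4 use a simple two-sample comparison with one covariate. They illustrate scale and do not represent the repeated-measures model.

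**The case against.** **What stands.**

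- Leaving gestational age out of the three-group model is defensible because of the aliasing in step 5. The gap is the lack of a committed adjusted contrast within the preterm infants.
- Both preterm groups share the five criteria and one neonatal unit, and section 3 says they are recruited by the same strategy. This limits differences, though the discharge preference and the database route weaken it and neither fixes gestational age. SES may gain some indirect balance if full-term infants are matched to both preterm groups, so gestational age and birth weight are the clearer gap.
- The root weakness is non-random assignment. Adjustment for three variables cannot cure selection that is not measured.

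**Stronger readings the protocol does not support.**

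- A reader might infer that the contrast is in fact confounded, or that the strongest predictors have been left out. No imbalance is known yet, and the protocol does not rank predictors.
- The statement "Random sampling is neither feasible nor appropriate in this context" might be taken as a refusal to randomise infants to WS or SC. It concerns drawing a sample from a population. The evidence on assignment is the entry routes and the absence of any randomisation procedure.
- The matching sentence might be read as a claim about the intervention effect. It does not say so, and demographic matching is relevant to the preterm versus full-term comparison, which is also planned.

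**What does not stand.** Planned secondary analyses and pre-registration are not an answer while the stated primary model excludes the covariates and the secondary work is described only as exploring their effects.

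**Conclusion.** The concern holds in this form: the WS-SC contrast is open to confounding by measured variables, and the protocol expressly keeps them out of its primary models. Under the assumed correlations (0.2 to 0.4) and imbalances (0.3 to 0.5 SD), the bias is 0.06 to 0.20 SD, or 10% to 34% of d = 0.59, and the nominal 5% test rejects about 6% to 14% of the time under no effect. The low end is close to nominal. The true value could lie outside the range, since the protocol states neither quantity.

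A reader might expect adjustment to raise power as well. At 40 per group and d = 0.59 the same assumptions give 0.73 to 0.80 against 0.74, so that is not assured. The point is worth settling before pre-registration fixes the unadjusted model as primary.

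**What to change.** 1. Prespecify, as the primary WS-SC estimate, a contrast fitted in preterm infants only and adjusted for gestational age, birth weight for gestational age, and SES. For looking times include covariate × stimulus type terms. Report the unadjusted model as a sensitivity analysis.
2. Do not simply add gestational age to the three-group model.
3. Check whether the gestational-age slope differs between WS and SC, and say in advance how the contrast will be reported if it does.
4. State where gestational age and birth weight will come from, for example the parent questionnaire. Section 7.6 says the research team will access no medical data, and no source for birth weight is named.
5. Limit the matching sentence to the preterm versus full-term comparison.

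**Cost.** Wording, a few degrees of freedom, and possibly a small loss of precision if the groups turn out imbalanced (variance ratio 1.02 in the least favourable row of step 4). The covariates are already intended for secondary analysis, so the added collection burden should be small once the source is settled. Selection through the discharge preference and the database route would remain where it is not captured by these covariates, and should be stated as a limitation.
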